Statistical Analysis Plan

Protocol Title:	An Open-label, Ascending Multiple-dose Study to Evaluate Safety, Tolerability, Pharmacokinetics, and Pharmacodynamics of Romosozumab in Children and Adolescents With Osteogenesis Imperfecta		
Short Protocol Title:	Enter Short Protocol Title		
Protocol Number:	20160227		
NCT Number:	N/A		
Authors:			
Sponsor:	Amgen Inc. [name]		
SAP Date:	Document Version Date		
	Original (v1.0) Amendment 1 (v2.0)	12 August 2020 15 April 2023	

Version Number	Date (DDMMMYYYY)	Summary of Changes, including rationale for changes
Original (v1.0)	12Aug2020	
Amendment 1 (v2.0)	15Apr2023	 Section 6.4: replace the PD analysis set with BTM analysis set. Subjects should have least a baseline BTM measurement of interest and at least 1 post-baseline BTM measurement of interest. Section 8.3: table 8.1 is removed. Missing stop date of AE or CM will not imputed. Imputation for start date of AE or CM is outlined in Appendix B.

 Section 9.2: The disposition of all randomized subjects will be tabulated by cohort is replaced with "The disposition of all subjects will be tabulated by cohort".
 4. Section 9.4: unit of BMI is revised to kg/m². (Yes, No) is removed from use of vitamin D and calcium. Nonvertebral fracture is added for fracture history and the definition of historical nonvertebral fractures is added as well. The error reference source for section 6.1 is addressed.
 Section 9.5.2: add reference hyperlink for Letocha et al, 2005, Rauch et al, 2009 and Ward et al, 2011.
 Section 9.5.2: Graphs showing summary statistics (actual value and change) of BMD Z-score, and percent change from baseline of BMD at lumbar spine over time by visit for age groups will be provided.
 Section 9.6.1: Subject listing of treatment-emergent adverse event will be provided. summary for subject incidence of adverse event is added. Serious cardiovascular event will be identified using cardiac and vascular SOC in MedDRA and be summarized as EOI.
8. Section 9.6.2: Graphs depicting summary statistics (change or percent

 change from baseline) for each parameter over time will be provided. 9. Section 9.6.6: Shifts in severity grades of laboratory parameters will not be assessed. Evaluation for Hy's Law and definition is added.

T _{max}	time to C _{max}

1. Introduction

The purpose of this Statistical Analysis Plan (SAP) is to provide details of the statistical analyses that have been outlined within the protocol for study 20160227, Romosozumab dated 28 February 2023. The scope of this plan includes the primary analysis that is planned and will be executed by the Amgen Global Biostatistical Science department unless otherwise specified.

2. Objectives, Endpoints and Hypotheses

2.1 Objectives and Endpoints

Objectives	Endpoints		
Primary			
 To evaluate the pharmacokinetics (PK) profile following multiple SC doses of romosozumab in children and adolescents with OI 	 Romosozumab serum PK parameters maximum-observed concentration (C_{max}), time to C_{max} (t_{max}), area under the curve (AUC), and terminal half-life (t_{1/2}) 		
Secondary			
 To evaluate the safety, tolerability, and immunogenicity profile following multiple SC doses of romosozumab in children and 	 Treatment-emergent adverse events, including events of injection site reactions and changes in cranial nerve function 		
 adolescents with OI To evaluate the pharmacodynamic (PD) profile following multiple SC doses of romosozumab in children 	 Vital signs, electrocardiograms, physical examinations and safety laboratory tests, including serum calcium and phosphorous 		
and adolescents with OI	 Incidence of antiromosozumab antibodies 		
	 Actual value and percent change from baseline of bone turnover markers including serum P1NP and serum CTX measurements 		
	 Actual value and percent change from baseline of lumbar spine BMD, bone mineral content (BMC), and bone area 		
	The percent change from baseline in BMD Z-score at lumbar spine		

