The subject incidence of all adverse events will be tabulated by body system organ class and preferred term for each dose cohort. Clinical laboratory, electrocardiogram, and vital sign data will be listed and summarized as appropriate. The incidence(s) and percentage of subjects who develop anti-romosozumab antibodies (binding and, if positive, neutralizing) at any time will be tabulated. Graphical summaries of the data over time may also be provided for the raw data and percent change from baseline. The change from baseline in BMD Z-score at lumbar spine will be checked against the meta-analysis result from historical controls (Letocha et al, 2005; Rauch et al, 2009; Ward et al, 2011).

For a full description of statistical analysis methods, please refer to Section 10.

Sponsor:

Amgen Inc. [name] [contact] [contact]

Study Design and Treatment Schema

DLRM 1 will be conducted after 2 subjects in cohort 1 complete 6 weeks on study. DLRM 1 will enable enrollment into cohorts 2 and 3. Enrollment into cohort 3 may begin after enrollment into cohort 1 is complete.

DLRM 2a may be conducted if escalation to the mg/kg dose level is deemed necessary based on available PK and PD data from cohorts 1 and 3. If necessary, DLRM 2a will be conducted after 2 subjects in cohort 3 complete 6 weeks on study. DLRM 2a will enable enrollment into cohort 5. Enrollment into cohort 5 may begin after enrollment into cohort 3 is complete.

DLRM 2b will be conducted after 2 subjects in both cohorts 2 and 3 complete 6 weeks on study. DLRM 2b will enable enrollment into cohort 4. Enrollment into cohort 2 is complete.

DLRM 3 may be conducted if escalation to the mg/kg dose level is deemed necessary based on available PK and PD data from cohorts 1 through 4. If necessary, DLRM 3 will be conducted after 2 subjects in both cohorts 4 and 5 complete 6 weeks on study. DLRM 3 will enable enrollment into cohort 6. Enrollment into cohort 6 may begin after enrollment into cohort 4 is complete.

DLRM indicates dose level review meeting; SC, subcutaneous.

Study Glossary

Abbreviation or Term	Definition/Explanation
ALP	alkaline phosphatase
ALT	alanine aminotransferase
AP	Anteroposterior
AST	aspartate aminotransferase
AUC	area under the curve
BMD	bone mineral density
BP	bisphosphonate
ВТМ	bone turnover markers
C _{max}	maximum-observed concentration
COL1A1	collagen type I alpha 1
COL1A2	collagen type I alpha 2
CRF	case report form

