10.1.1.2 Secondary Endpoints

- Treatment-emergent adverse events, including events of injection site reactions and changes in cranial nerve function
- Vital signs, electrocardiograms, physical examinations and safety laboratory tests, including serum calcium and phosphorous
- Incidence of antiromosozumab antibodies
- Bone turnover markers including serum P1NP and sCTX measurements
- Lumbar spine BMD, bone mineral content (BMC), bone area, and BMD Z-score as assessed by DXA

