10.4.3.2 BMD DXA

Actual value and percent change from baseline in BMD at the AP lumbar spine will be descriptively summarized at each visit for each dose cohort. The change from baseline in BMD Z-score at lumbar spine will be checked against weighted estimated mean (SE) of 0.01 (0.09) (95%CI: -017, 0.18) based on meta-analysis result from historical controls

(Letocha et al, 2005; Rauch et al, 2009; Ward et al, 2011). The results from the historical controls will contextualize the observed BMD results at the dose level review meeting.

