5.6 Arithmetic Calculations

Change from Baseline

The arithmetic difference between a post-baseline value and the baseline value:

Change (absolute) from Baseline = (post-baseline value – baseline value)

Change (percent) from Baseline = [(post-baseline value – baseline value) / baseline value] x 100

Body Mass Index (BMI)

Body Mass Index will be calculated using the following formula:

BMI (kg/m^2) = weight $(kg) / [height (cm)/100]^2$

Subject Incidence for AEs

The subject incidence for a given event in a given time period is defined as the number of subjects with at least 1 reported occurrence of the event divided by the number of subjects who are at risk for having the event at the beginning of the given time period. For subjects with multiple occurrences of the same event, the event will only be counted once per subject.

6. Analysis Sets

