9.5.2 Analyses of Secondary Efficacy Endpoint(s)

Actual value and percent change from baseline in BMD, BMC and bone area at the AP lumbar spine will be descriptively summarized at each visit for each dose cohort. The change from baseline in BMD Z-score at lumbar spine will be checked against weighted estimated mean (SE) of 0.01 (0.09) (95%CI: -017, 0.18) based on meta-analysis from historical controls (Letocha et al, 2005; Rauch et al, 2009; Ward et al, 2011). Graphs showing summary statistics (actual value and change from baseline) of BMD Z-score, and percent change from baseline of BMD at lumbar spine over time by visit for age groups will be provided. The results from the historical controls will contextualize the observed BMD results at the dose level review meeting. The BMD analysis set will be used to for these analyses.

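### SAP 2.1 defines the BMD Z-score endpoint as a percent change, but the planned analysis uses absolute change, and percent change reverses sign whenever the baseline score is negative

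*SAP*

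**What the plan says.** The endpoint table in SAP 2.1 gives percent change as the only form of the Z-score endpoint: "The percent change from baseline in BMD Z-score at lumbar spine".

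The analysis passages say something else:

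- SAP 9.5.2 reserves percent change for the other three DXA measures: "Actual value and percent change from baseline in BMD, BMC and bone area at the AP lumbar spine will be descriptively summarized". Z-score is not among them.
- SAP 9.5.2 then plans "Graphs showing summary statistics (actual value and change from baseline) of BMD Z-score", and in the same sentence gives BMD a different metric: "percent change from baseline of BMD at lumbar spine over time by visit for age groups will be provided".
- The Protocol synopsis, under Statistical Considerations, states: "The change from baseline in BMD Z-score at lumbar spine will be checked against the meta-analysis result from historical controls". Protocol 10.4.3.2 and SAP 9.5.2 repeat this and give the comparator as a weighted mean of 0.01 with standard error 0.09.

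Protocol 10.1.1.2 names the measure without any change metric, "Lumbar spine BMD, bone mineral content (BMC), bone area, and BMD Z-score as assessed by DXA", so it neither supports nor contradicts SAP 2.1.

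SAP 5.6 defines change from baseline, with no qualifier, as the post-baseline value minus the baseline value. It defines "Change (percent) from Baseline" as that difference divided by the baseline value and multiplied by 100. The denominator carries its sign.

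**The concern.** The endpoint as defined has no matching analysis, and the analysis as planned has no matching endpoint. Of the two versions, the one in the endpoint definition is the one that fails. A Z-score can be negative, zero or positive, so a ratio to its baseline has no consistent meaning.

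If a table or an endpoint label were built from SAP 2.1 as worded, a child with a negative baseline who improved would be reported as having lost ground. The result also could not be set beside the historical-control value, which is in Z-score units. This is the one DXA measure in the plan with an external comparator, and the stated hypothesis is that PD results, including effects on BMD, will help select the dose for the next paediatric study.

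**Working it through.** **Inputs.** The two change formulas come from SAP 5.6. The historical-control mean 0.01, SE 0.09 and 95% CI, printed as -017 to 0.18, come from Protocol 10.4.3.2 and SAP 9.5.2. The cohort size of 4 comes from SAP 3.1. The documents give no baseline Z-scores and no expected gain, so every baseline and gain below is an assumption.

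**Step 1: the plan's own figure.** 0.01 ± 1.96 × 0.09 = 0.01 ± 0.176, which gives -0.166 to 0.186. The lower limit rounds to -0.17, so the printed -017 is a lost decimal point. The upper limit would round to 0.19 against 0.18 printed. Unrounded inputs explain this: 0.007 ± 1.96 × 0.089 gives -0.167 to 0.181. The benchmark is therefore an absolute difference in Z-score units.

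**Step 2: sign.** Let B be the baseline and P the later value. Absolute change is P - B; percent change is 100 × (P - B)/B. If B < 0, the two always have opposite signs. For the same gain of 0.5:

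| Baseline | Later value | Absolute change | Percent change |
|---|---|---|---|
| -3 | -2.5 | +0.5 | -16.7% |
| -2 | -1.5 | +0.5 | -25.0% |
| -1 | -0.5 | +0.5 | -50.0% |
| -0.1 | 0.4 | +0.5 | -500% |
| 0.1 | 0.6 | +0.5 | +500% |
| 1 | 1.5 | +0.5 | +50.0% |

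A fall from -2 to -2.5 gives 100 × (-0.5)/(-2) = +25%. At B = 0 the percent change is undefined.

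**Step 3: a cohort of four (assumed baselines -4, -3, -2, -1).** If each child gains 0.5, the percent changes are -12.5, -16.7, -25.0 and -50.0: mean -26.0%, median -20.8%. A gain of 0.2 gives mean -10.4% and median -8.3%; a gain of 1.0 gives mean -52.1% and median -41.7%.

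One baseline near zero can dominate. If all four gain 0.5, baselines of -3, -2, -1 and +0.2 give a mean of (-16.7 - 25.0 - 50.0 + 250.0)/4 = +39.6%. Replacing +0.2 by -0.1 gives (-16.7 - 25.0 - 50.0 - 500.0)/4 = -147.9%. The mean absolute change is +0.5 in both.

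**Step 4: the benchmark on the percent scale.** At a baseline of -3, 0.01 becomes 100 × 0.01/(-3) = -0.3%, and the limits -0.17 and 0.18 become +5.7% and -6.0%. At -1 they become -1.0%, +17% and -18%. The limits swap order and the width depends on the baseline chosen, so the historical value has no single percent equivalent.

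**The case against.** The strongest reply is that the methods section already has it right. SAP 5.6 defines unqualified change as an arithmetic difference, SAP 9.5.2 applies that to the Z-score both in the historical check and in the graphs, and the Protocol agrees. No methods passage asks for a percent change in Z-score, so harm would require someone to program from the endpoint table against the methods text. On this view it is a wording slip in a descriptive secondary endpoint.

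Much of this stands. It limits the impact, and the percentages above show how the metric behaves rather than what this trial would report, because they rest on assumed baselines. It is also fair that SAP section 10 had nothing to declare here, since the SAP and Protocol analyses of Z-score match.

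The reply does not remove the conflict. SAP 2.1 is where the SAP defines its endpoints, and its wording contradicts the planned analysis. The sign reversal needs no assumed figures, only a negative baseline.

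**Conclusion.** The point holds. SAP 2.1 is wrong as written: it defines the Z-score endpoint on a scale that no analysis passage uses and that reverses direction for any negative baseline. The reversal is algebra from the SAP's own formula. That many baselines will be negative is plausible, because the Protocol describes the disease as one of low bone mass, but the documents give no baseline Z-scores and set no Z-score entry criterion.

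The consequence is modest. No test, sample size or decision rule uses the endpoint. Nor is anything claimed about the dose level review meetings, where the text gives the role of context to the historical-control results. The error should be corrected before outputs are produced, because it could otherwise present improvement as loss.

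**What to change.** In SAP 2.1, replace the Z-score line with: *Actual value and change (absolute) from baseline in BMD Z-score at lumbar spine*. This matches SAP 9.5.2 and Protocol 10.4.3.2. SAP 5.6 needs no change.

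Optionally, add a sentence to SAP 9.5.2 that Z-score actual values and absolute changes are summarised by dose cohort and visit. The Z-score graphs there are by age group, and SAP 9.1 provides cohort summaries only where appropriate. The Protocol synopsis already calls for summaries by dose cohort and time point, so this second sentence is a clarification and the correction does not depend on it.

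The cost is one line of SAP text, or two with the option, with no effect on data collection, patients or timelines.

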2.2 Hypotheses and/or Estimations

Romosozumab PK and PD, including the effects on bone mineral density (BMD) and bone turnover markers (procollagen type 1 N-terminal propeptide [P1NP] and serum collagen type 1 cross-linked C-telopeptide [CTX]), will aid in the selection of the dose for the subsequent efficacy and safety study in pediatric subjects with OI. Romosozumab will be safe and well tolerated following multiple SC dose administrations in children and adolescents with OI.

3. Study Overview

3.1 Study Design

This is a multicenter, open-label, ascending multiple-dose study to evaluate romosozumab in ambulatory children (5 to less than 12 years of age) and adolescents (12 to less than 18 years of age) with OI.

At least 16 subjects will be enrolled into sequential cohorts 1 to 4 (4 per cohort). All subjects will receive a total of SC doses of romosozumab administered every **SC** and 2 (5 to less than 12 years of age) will be administered romosozumab mg/kg SC SC Subjects in cohorts 3 (12 to less than 18 years of age) and 4 (5 to less than 12 years of age) will receive romosozumab mg/kg SC SC Subjects are insufficient at and mg/kg, at least 4 subjects each will enroll into cohorts 5 (12 to less than 18 years of age) and 6 (5 to less than 12 years of age) and will receive romosozumab mg/kg SC SC SC Subjects to less than 12 years of age) and 6 (5 to less than 12 years of age) and will receive romosozumab mg/kg SC SC Subjects will receive daily supplementation with calcium and vitamin D.

The planned dose levels and cohorts are described in the below table.

Cohort #	Age Group (years of age)	Dose*	Dosing Day	N (active)
1	12 to less than 18			4
2	5 to less than 12			4
3	12 to less than 18			4
4	5 to less than 12			4
5 (optional)	12 to less than 18			4
6 (optional)	5 to less than 12			4

 Table 3-1.
 Planned Dose Levels

* All doses will be administered subcutaneously

As a precautionary measure consistent with pediatric research, dose cohorts, starting with the lowest dose level, will be recruited so that adolescents 12 to less than 18 years of age will be enrolled first (n = 4) at each dose level, before children 5 to less than 12 years of age (n = 4) for the same dose level.

A dose level review meeting (DLRM) will be held to review safety data for the purposes of making recommendations before escalation to the next higher dose or expansion to a younger age cohort. The dose level review team (DLRT) will be composed of, at a minimum, the investigators actively enrolling subjects at the time of the meeting (ie, have subjects in screening or already enrolled), the Amgen Medical Monitor, and Amgen Global Safety Officer or designated safety scientist, Amgen Clinical Research Study Manager or designee, and biostatistics representative or designee. Additional members may be added as needed (eg, PK scientist). The DLRT voting members include the principal investigator or designee, Amgen Medical Monitor and Amgen Global Safety Officer or designee. The DLRT voting members are responsible for making dosing recommendations, which may include escalation to the next planned dose, escalation to an intermediate dose (a dose lower than the next planned dose), de-escalation to a lower dose; continuation, delay, or termination of dosing; or repetition or expansion of a cohort. Clear stopping rules will be followed, and ad hoc DLRMs will be held if necessary. All available study data, including demographics, medical history, concomitant medications, adverse events, electrocardiograms, vital signs, and clinical laboratory test results will be reviewed. The medical monitor will review data on an ongoing basis throughout the duration of the study.

Investigators who are not actively enrolling subjects at the time of the DLRM will not participate in the DLRM. They will be informed of the DLRT recommendations.

DLRMs will take place at the following time points:

- DLRM 1
 - After 2 subjects in cohort 1 complete 6 weeks on study
 - o DLRM 1 will enable enrollment into cohorts 2 and 3
- DLRM 2a
 - May be conducted if escalation to the mg/kg dose level is deemed necessary based on available PK and PD data from cohorts 1 and 3
 - If necessary, DLRM 2a will be conducted after 2 subjects in cohort 3 complete 6 weeks on study
 - o DLRM 2a will enable enrollment into cohort 5
- DLRM 2b
 - After 2 subjects in both cohorts 2 and 3 complete 6 weeks on study
 - o DLRM 2b will enable enrollment into cohort 4
- DLRM 3
 - May be conducted if escalation to the mg/kg dose level is deemed necessary based on available PK and PD data from cohorts 1 through 4

- If necessary, DLRM 3 will be conducted after 2 subjects in both cohorts 4 and 5 complete 6 weeks on study
- o DLRM 3 will enable enrollment in cohort 6

3.2 Sample Size

The sample size is based on practical considerations. At least 16 subjects (or 24 depending on emerging results) will be enrolled into the study.

3.3 Adaptive Design

Adaptive design is not applied in the study.

4. Covariates and Subgroups

4.1 Planned Covariates

No covariate is planned in the study.

4.2 Subgroups

No subgroup analysis is planned.

5. Definitions

5.1 Basic Definitions

Treatment-emergent Adverse Events (TEAE)

Adverse Events (AEs) starting on or after first dose of investigational product as determined by the flag indicating if the adverse event started prior to the first dose on the Adverse Events eCRF and up to the end of study date.

Treatment-emergent Serious Adverse Event (TESAE)

Treatment-emergent adverse events indicated as serious on the Events eCRF

